**Check Documents being submitted herewith to committee:**

1. Summary : Attached
2. Umbrella proposal initially : NA
3. Protocol and CRF : Attached
4. Informed consent form for subject : Attached
5. Verbal consent form for subjects : NA
6. Procedure for Maintaining Confidentiality : Attached
7. Schedule of the study : Attached

**Circle the appropriate answer to each of the following**

(If not Applicable write NA)

1. Source Population:			4. Are subjects clearly informed about:		
(a) Ill Subjects	√Yes	No	(a) Nature and purpose of the study	√Yes	No
(b) Non* ill subjects	Yes	√No	(b) Procedures to be followed including alternatives used	√Yes	No
(c) Minors or persons under guardianship	Yes	√No	(c) Physical risks	√Yes	No
			(d) Private questions	√Yes	No
2. Does the study involve:			(e) Invasion of the Body	√Yes	No
(a) Physical risks to subjects	√Yes	No	(f) Benefits to be Derived	√Yes	No
(b) Social risks	Yes	√No	(g) Right to refuse to participate or withdraw from the study	√Yes	No
(c) Psychological risks to subjects	Yes	√No	(h) Confidential handling of data	√Yes	No
(d) Discomfort to Subjects	√Yes	No	(i) Compensation where there are risks or loss of working time or privacy is involved in any particular procedure	√Yes	No
(e) Invasion of the body	√Yes	No			
(f) Invasion of privacy	Yes	√No			
(g) Disclosure of information damaging to subject or others	Yes	√No	5. Will informed consent be required		
			(a) From subject	√Yes	No
			(b) From parent or Guardians	Yes	√No
3. Does the study involve:					
(a) Use of records (hospital, medical, death, birth or other)	Yes	√No	6. Will precautions will be taken to protect anonymity of subjects	√Yes	No
(b) Use of fetal tissue or abortus	Yes	√No			
(c) Use of organs or body fluids	Yes	√No			

## PART-C

### **Title: Effects of Doxercalciferol Compared to Calcitriol For Lowering Parathyroid Hormone Level in Patients on Hemodialysis**

#### Summary

**Background:** Secondary hyperparathyroidism (SHPT) in advanced CKD results from phosphate retention and vitamin D deficiency, leading to elevated PTH levels that increase bone and cardiovascular risks. Active vitamin D analogs such as calcitriol and doxercalciferol help manage SHPT by suppressing PTH, although they differ in pharmacokinetics and effects on mineral metabolism. Intravenous formulations may provide better bioavailability and adherence than oral options, particularly in dialysis patients with absorption challenges. **Aims:** The study aims to compare the effectiveness of intravenous doxercalciferol and oral calcitriol in reducing parathyroid hormone (PTH) levels in patients undergoing hemodialysis. **Materials and Methods:** A Randomized control trial will be conducted in the Department of Nephrology of Chittagong Medical College Hospital including 98 adult hemodialysis patients with secondary hyperparathyroidism. Participants will receive either intravenous Doxercalciferol or oral Calcitriol. **Statistical analysis:** Continuous variables will be presented as mean  $\pm$  standard deviation, and categorical variables as frequencies and percentages. Independent t-tests will be used to compare means between groups, while chi-square or Fisher's exact tests will analyze categorical outcomes. The primary analysis will be an intention to treat or per protocol which one is applicable and will be analysis performed with SPSS-27.0. A p-value of less than 0.05 will be considered statistically significant for all analyses. Distributions will be expressed by mean and standard deviation for continuous variables and by frequency and percentage for qualitative variables. **Conclusion:** If intravenous doxercalciferol demonstrates improved effectiveness and a better safety profile, it could help physicians manage secondary hyperparathyroidism in hemodialysis patients more efficiently.

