**Withdrawal criteria:**

- Drug intolerance or patient refusal to continue medication due to adverse effects like nausea, anorexia, vomiting, etc.
- The patient wanted to withdraw himself from the study.
- If any participant became pregnant during the study period.

**5.10 Data collection instrument:** A structured pretested case record form.

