**5.11 Data collection procedure:**

All ESRD patients on hemodialysis will be consecutively and prospectively screened according to the above inclusion and exclusion criteria to identify eligible participants for randomization. Eligible patients and their legal relatives will then fully explain the study protocol, their role in the study, and the risks of the study. They will be informed of their right to withdraw from the study at any stage. After getting written informed consent, they will be finally enrolled in the study.

- **Baseline evaluation:** Baseline data will be collected at enrollment, including demographic and anthropometric variables such as age, sex, monthly income, height, weight, and body mass index (BMI). These variables will be recorded systematically for both groups to ensure proper group characterization and comparability. In addition, clinical information will be documented, focusing on the presence of comorbidities such as diabetes mellitus (DM) and hypertension (HTN). Baseline serum calcium, serum phosphate, iPTH will be recorded in the case record form. washout period of calcitriol will be conducted prior to randomization.
- **Randomization:** After consenting, eligible individuals will be recruited consecutively and randomly assigned in 1:1 ratio (block size of four), with a computer-generated randomization list, to one of the two treatment arms (Experimental group and Control group). Group 1 (Control Group) Will received oral calcitriol alone with standard treatment of CKD. Group 2 (Experimental Group) will received post-hemodialysis intravenous (IV) doxercalciferol alone with standard treatment of CKD. All participants, regardless of group allocation, who are on calcium acetate or sevelamer will continue these medications at their existing doses throughout the study period.
- **Blinding:** Blinding of the study medication is not possible because of resource limitations. It is an open-label study and both the researcher and the subject know about the drugs they are receiving.

**Sample Collection procedure:** Blood samples will be collected pre-dialysis after an overnight fasting period, with all aseptic precaution 5 mL of venous blood drawn into appropriate vacutainers.

- iPTH will be measured using a chemiluminescence immunoassay (CLIA).
- Serum calcium and phosphate will be analyzed using colorimetric methods on a Beckman Coulter AU480 or equivalent validated clinical chemistry analyzer.

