All laboratory analyses will be conducted in an ISO-certified laboratory, ensuring accuracy and standardization of results.

**Treatment:** The treatment phase will last for twelve weeks. Experimental subjects will receive an intravenous loading dose of doxercalciferol 4 micrograms after dialysis, in addition to their standard routine medications. Each Dose of doxercalciferol will be given after skin sensitivity test. Skin sensitivity test will be performed by a small amount of doxercalciferol inject intradermally → wait 10-15 minutes → see for localized swelling and redness. Though skin sensitivity test negative despite patients may developed anaphylactic reaction, Then following measure will be taken. Prevent further contact with allergen, ensure airway patency, anti histamine, hydrocortisone, nebulize with sulbutamol, adreline, i/v fluids. Patients in the control group will receive oral calcitriol 0.25 micrograms once daily, along with their standard routine medications.

**Evaluation of the patient at 6 Weeks:** The patients will be followed up at 6 weeks ( $\pm 2$  days) and will instructed to report immediately in case of any advance events following consumption of the drug. Tolerability will be assessed using an adverse event profile (adverse events, serious adverse events). Safety population consist of subjects who receive at least one dose of study medication. Body weight and sitting blood pressure will be evaluated. patients will be removed if any of the withdrawals mentioned above are observed, and appropriate management will be initiated in the nephrology department of CMCH.

**Follow –up and outcome assessment:** All the patients will be examined again after 12 weeks ( $\pm 2$  days) The same biochemical parameters—serum calcium, serum phosphate, iPTH,—will be reassessed under the same collection and analysis protocols. These follow-up results will be compared with baseline values to evaluate the relative efficacy of IV doxercalciferol versus oral calcitriol in controlling SHPT and maintaining mineral balance. All data, including demographic, clinical, and laboratory results, will be systematically documented in a Case Record Form (CRF) to ensure completeness and integrity of the dataset.

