- If a patient does not return for a scheduled visit, every effort will be made to contact the patient. If possible, every effort will be made to document patient outcomes in any circumstance. The Investigator will enquire about the reason for withdrawal, request that the patient return all unused study medication, ask that the patient return for a final visit, if applicable, and follow up with the patient regarding any unresolved adverse events.

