#### Outcome

	Complete the study per the Protocol 0= No 1= yes
	If not reason for drop-out 1. Adverse experience 2. Failure to return for follow-up 3. Patients refuse treatment 4. Patient died 5. Non-co-operation 6. Insufficient therapeutic response

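### The protocol leaves the primary analysis population open between ITT and per protocol in an open-label trial, and does not say whether patients who stop study drug contribute a week-12 iPTH

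*Protocol*

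**What the plan says.** **Population.** The statistical paragraph of the Summary (Part C) states: "The primary analysis will be an intention to treat or per protocol which one is applicable". Section 5.12 (Data analysis) lists tests but no population. The only analysis set defined anywhere is the safety population, in the 6-week paragraph of section 5.11.

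**Blinding.** Section 5.11: "It is an open-label study and both the researcher and the subject know about the drugs they are receiving".

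**Withdrawal.** The withdrawal criteria are:
- "Drug intolerance or patient refusal to continue medication due to adverse effects like nausea, anorexia, vomiting, etc";
- the patient's own wish to leave;
- pregnancy.

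The 6-week paragraph of section 5.11 adds that "patients will be removed if any of the withdrawals mentioned above are observed". It does not say whether this means removal from drug, from visits or from analysis.

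**Outcomes after withdrawal.** The end of section 5.11 says that, where possible, "every effort will be made to document patient outcomes in any circumstance". It also has the investigator "ask that the patient return for a final visit, if applicable".

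**Case record form.** The Outcome page lists six reasons for drop-out. The sixth is "Insufficient therapeutic response", which is not among the withdrawal criteria.

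**When iPTH is measured.** Section 5.11 and the case record form schedule it at baseline and week 12 only. The 6-week visit covers adverse events, body weight and blood pressure.

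**The concern.** A primary analysis should be fixed before anyone can see what it yields. Here the protocol writes the choice into the rule itself. It does not say what makes one population applicable, when that is decided, or by whom. With open-label treatment, nothing in the document stops the choice from being made after both results are known. Two chances at significance for one hypothesis raise the false-positive rate. If per-protocol exclusion is related to iPTH, the second chance is also a biased one.

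The second issue is whether an ITT analysis will have the data it needs. A patient removed at 6 weeks has no scheduled iPTH after baseline unless a week-12 sample is still drawn, and the text neither requires nor rules out that sample. The arms differ in route, and the skin test applies only to doxercalciferol, so reasons for stopping may differ by arm. The documents do not establish that they will.

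**Working it through.** The protocol gives no figure for the effect of choosing between populations. The reference value is its own two-sided 5% level.

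**Inputs from section 5.8:** two-sided alpha 0.05; 49 per arm; 15% dropout allowance; SDs of iPTH 42 (oral) and 90 (doxercalciferol); planned difference 342 − 279 = 63 pg/mL.

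The 49 per arm is taken as the stated target. The printed formula does not reproduce the 42.8 behind it: (1.96 + 0.85)² × (42² + 90²) / 63² = 19.6, or 26.1 with the stated 1.28. That is a separate matter and does not bear on this point.

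**Assumptions, not in the documents:** no true difference; week-12 iPTH available for all 98 patients; per protocol drops 7 per arm (15% of 49 = 7.35) in any arm that loses patients; the result is called positive if either set gives p < 0.05.

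**Step 1: exclusion at random, analytic check.** When per protocol is a random 42 of each 49, its test statistic correlates with the ITT statistic at √(42/49) = 0.926. For two standard normal statistics with that correlation, the probability that at least one exceeds 1.96 in absolute value is 0.068. Choosing the better set therefore gives 6.8% instead of 5%.

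**Step 2: simulation.** 8,000 null trials per scenario, Welch t-test. Results are for SDs 42/90, with equal SDs of 70.2 in brackets (70.2 = √((42² + 90²)/2)).

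| Assumed per-protocol exclusion | ITT alone | Either set |
|---|---|---|
| Random, both arms | 4.8% (5.0%) | 7.0% (6.8%) |
| Moderately related to high iPTH, both arms | 4.9% (5.2%) | 9.1% (7.1%) |
| Moderately related in doxercalciferol arm, random in the other | 4.6% (4.9%) | 14.3% (11.2%) |
| Extreme: 7 highest iPTH values lost from doxercalciferol arm, random in the other | 4.8% (4.8%) | 45% (28%) |

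Moderately related means a correlation of 0.5 between iPTH and the tendency to be excluded. The simulation standard error is about 0.2 to 0.6 percentage points. The first row agrees with the analytic value. The other rows show how the answer depends on an exclusion pattern that the protocol does not give.

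**Step 3: shift in one arm's mean in the extreme case.** If the highest fraction q of a normal distribution is lost, the mean falls by SD × φ(z) / (1 − q), where z is the upper-q normal quantile.
- SD 90: q = 10% gives 90 × 0.1755 / 0.90 = 17.5 pg/mL; q = 15% gives 90 × 0.2332 / 0.85 = 24.7 pg/mL. These are 28% and 39% of 63.
- SD 42: the same formula gives 8.2 and 11.5 pg/mL, or 13% and 18% of 63.

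These are upper limits under one-sided, perfectly selective loss. They are not estimates for this trial.

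**Step 4: the withdrawal texts side by side.** Section 5.11 says removed at the 6-week paragraph and says at its end that outcomes are sought. Between them they leave two questions open: whether week-12 iPTH is drawn after study drug stops, and whether that value is used in the primary analysis.

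**The case against.** **A statistical analysis plan may settle the population.** If the protocol were silent, that would be a full answer. It is not silent: it states a rule, and the rule is an open choice. This objection does not stand.

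**The text does not abandon withdrawn patients.** A reader might infer that they are dropped from follow-up, so that their week-12 iPTH cannot exist and ITT cannot be run. The documents do not support that. The 6-week paragraph does not say what patients are removed from, the end of section 5.11 promises every effort to document outcomes and asks for a final visit, and the follow-up paragraph says all patients are examined at 12 weeks. This objection stands. What remains is an ambiguity between texts.

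**Poor response is not a ground for removal.** A reader might infer from the sixth case record form code that the trial will shed its poor responders. That code records why someone left and authorises nothing. This also stands. The mismatch with the withdrawal criteria is real but small.

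**The two problems cannot both come from the same patients.** The 7% needs week-12 values for those whom per protocol excludes. If those values are missing, a complete-case ITT and per protocol largely coincide, and most of the inflation from choosing disappears. This is correct, so the 7% holds only under its stated condition, and missing data is a separate risk.

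**The large figures rest on invented exclusion patterns.** That is fair. The SDs in section 5.8 describe iPTH level and not response, and 90 belongs to one arm only.

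**Conclusion.** The point holds in two parts.

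1. The primary population is left to a later choice, without a rule, in an open-label trial, and nothing else in the protocol settles it. This follows directly from the text. Its size is about 7% type I error against 5%, given complete week-12 iPTH, 15% excluded at random, and the more favourable set being reported. Outcome-related exclusion would raise it, but neither the direction nor the size of such bias can be computed from the documents.

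2. The protocol does not say whether patients removed for a withdrawal criterion still give a week-12 iPTH or whether it counts in the primary analysis, and the case record form does not match the withdrawal criteria. This is a lack of clarity, with no calculable effect. It does not show that patients are lost or selected.

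The first part must be corrected before outcome data are seen, because a population named afterwards would not be credible.

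**What to change.** In the Summary and section 5.12, state that the primary analysis is ITT: all randomised patients, analysed as randomised. Define per protocol in advance and label it a sensitivity analysis. Name the method for missing week-12 iPTH.

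In section 5.11, state that week-12 iPTH, calcium and phosphate are sought from every patient who has not withdrawn consent to data collection, including those who have stopped study drug. Reconcile the withdrawal criteria, the 6-week paragraph, the text on missed visits and the case record form drop-out codes, so that stopping drug and leaving data collection are recorded separately. This sets no clinical stopping rule; when treatment stops remains for the investigators to specify.

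The cost is a few sentences, a case record form edit and a few extra week-12 samples. Most of these can be drawn at dialysis sessions, which the operational definitions put at twice weekly. The ITT estimate may be somewhat diluted by non-adherence. Values will still be missing for patients who die or do not return, which is why the missing-data method is needed. With ITT fixed as the only primary set, the simulated type I error is nominal within simulation error (4.6% to 5.8% across all scenarios run), and the target of 98 is unchanged.

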### **Specific objectives:**

1. To detect and compare the reduction of serum parathyroid hormone (PTH) levels following treatment with intravenous doxercalciferol and oral calcitriol in hemodialysis patients.
2. To assess the changes in serum calcium and phosphate levels associated with each treatment modality.
3. To evaluate the incidence of treatment-related hypercalcemia and hyperphosphatemia in both treatment groups.
4. To compare the adverse events and efficacy profiles of intravenous doxercalciferol and oral calcitriol in the management of secondary hyperparathyroidism in hemodialysis patients.

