### 5.8. Sample size:

To calculate sample size for case control, study the comparison between two means, the following formula was followed (Hoque, 2014)

$$n = \frac{(Z_a + Z_b)^2 \cdot (s_1^2 + s_2^2)}{(m_1 - m_2)^2}$$

Here,

$m_1$  = 342.0 (mean of iPTH in oral cholicalciferol group)

$m_2$  = 279.0 (mean of iPTH in intravenous doxercalciferol group)

$s_1$  = 42.0 (Standard deviation of oral cholicalciferol group)

$s_2$  = 90.0 (Standard deviation of intravenous doxercalciferol group)

$Z_a$  = Z value (two tail) of standard normal distribution at 95% confidence level or 5% level of significance = 1.96 (when  $\alpha = 0.05$  at 5% level of significance)

$Z_b$  = Z value at 90% power = 1.28 (when  $\beta = 0.1$  and Power =  $1 - \beta$ )

Therefore,

$$\begin{aligned} n &= \frac{(1.96 + 0.85)^2 \cdot \{(42.0)^2 + (90.0)^2\}}{(342.0 - 279.0)^2} \\ &= 42.8 \end{aligned}$$

This study is a follow-up study, necessitating a 15% increase in the sample size to compensate for dropout cases during the follow-up period. Consequently, the total sample size amounted to 49 cases, comprising 43 estimated sample size plus an additional 6.

Therefore, total sample size was 98 ( $49 \times 2$ ).

All values were taken from Aggarwal et al. (2011).

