#### **5.12. Data analysis:**

Statistical analysis will be performed using Statistical Package for Social Science (SPSS) version 27.0 (IBM Corp., Armonk, NY, USA). Baseline continuous variables such as age, monthly income, height, weight, BMI, blood pressure, duration of hemodialysis, and biochemical markers (serum calcium, phosphate, parathyroid hormone, and serum creatinine) will be expressed as mean  $\pm$  standard deviation (SD) or median with interquartile range (IQR) depending on data distribution, while categorical variables such as sex, presence of diabetes mellitus (DM), hypertension (HTN) use will be presented as frequencies and percentages. Normality of continuous variables will be assessed using the Shapiro-Wilk test. For comparison between the control and experimental groups, independent samples t-test or Mann-Whitney U test will be applied for continuous variables, depending on their distribution, and Chi-square test or Fisher's exact test will be used for categorical variables. Biochemical parameters (serum calcium, phosphate, PTH, and serum creatinine) at baseline and after 12 weeks of follow-up will be compared within each group using paired t-test or Wilcoxon signed-rank test as appropriate. A p-value of less than 0.05 will be considered statistically significant.

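### The protocol does not fix which iPTH comparison decides the trial, and its wording lets a within-arm test against baseline stand as evidence of relative efficacy at p<0.05

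*Protocol*

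**What the plan says.** The title, the hypothesis (3.2), the general objective (4.1) and the sample size (5.8) all concern PTH. No section labels an endpoint as primary. The Summary uses the word primary only for the choice of analysis set, which it leaves open between intention to treat and per protocol.

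The iPTH comparison is described differently from place to place:

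- Specific objective 1: "To detect and compare the reduction of serum parathyroid hormone (PTH) levels following treatment".
- Section 5.8 is sized on a difference in mean level. Its inputs are "342.0 (mean of iPTH in oral cholicalciferol group" and 279.0, described as the "mean of iPTH in intravenous doxercalciferol group".
- Section 5.11, on follow-up and outcome assessment: "These follow-up results will be compared with baseline values to evaluate the relative efficacy of IV doxercalciferol versus oral calcitriol".
- Section 5.12 gives a between-arm t-test or Mann-Whitney test for continuous variables, without saying whether the variable is the week-12 value or the change. It then gives paired tests of baseline against 12 weeks inside each arm.

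The significance rule appears twice. The Summary says "A p-value of less than 0.05 will be considered statistically significant for all analyses", and 5.12 closes with "A p-value of less than 0.05 will be considered statistically significant". The same rule therefore covers iPTH, calcium, phosphate, the incidence of hypercalcaemia and hyperphosphataemia, the adverse-event comparison and the within-arm tests.

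**The concern.** There are two separate weaknesses.

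First, a between-arm comparison of week-12 level and one of change from baseline are different tests. They can disagree in the same data, and the protocol supports both. If the choice is made after the results are known, the error rate is no longer 5%.

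Second, and more serious, 5.11 ties relative efficacy to comparison with baseline, and the only such test in 5.12 is made separately in each arm. A report could follow the text faithfully, find a significant fall with doxercalciferol and a non-significant one with calcitriol, and conclude that doxercalciferol is better. That pattern is not a comparison of the treatments, and it can arise easily when the two drugs are equal.

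The Summary's planned conclusion covers both effectiveness and safety, and 5.13 expects the results to guide the choice of drug. What counts as a positive result should therefore be fixed in advance.

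**Working it through.** **Inputs from the protocol.** Two-sided level: "Z value (two tail) of standard normal distribution at 95% confidence level or 5% level of significance = 1.96" (5.8). Means 342.0 and 279.0, SDs 42.0 and 90.0, and 43 per arm before the dropout allowance (5.8). iPTH, calcium and phosphate are recorded at baseline and 12 weeks (5.11 and the case record form).

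**Inputs that are assumptions.** Correlation r between baseline and week-12 iPTH of 0.3 to 0.7, and coefficient of variation of 0.26 to 0.5.

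**Step 1: the plan's own figure.** Section 5.8 reports n = 42.8. Its worked formula gives (1.96 + 0.85)² × (42² + 90²) / 63² = 7.8961 × 9864 / 3969 = 19.6. With the stated "Z value at 90% power = 1.28" it gives 10.4976 × 9864 / 3969 = 26.1. Neither reproduces 42.8. That is a separate error. I use 43 per arm only as the plan's own number, and false-positive rates under no difference hardly depend on it.

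**Step 2: level or change, between arms.** With equal variances at the two visits, the correlation between week-12 level and absolute change is √((1 − r)/2):

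| r | Correlation of level and change |
|---|---|
| 0.3 | 0.59 |
| 0.5 | 0.50 |
| 0.7 | 0.39 |

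The two tests overlap only in part. If they were independent, the chance that at least one reaches p<0.05 would be 1 − 0.95² = 9.75%. If they were identical, it would be 5%.

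Simulation under equal drugs (43 per arm, 20,000 trials per setting, normal data) gives:

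- Either test alone: 4.7% to 5.2%.
- At least one of the two: 8.6% to 9.3%.
- With the CV range above: 8.3% to 9.2%, of which 4.1% to 4.7% of trials favour doxercalciferol, against a nominal 2.5%.

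**Step 3: paired tests read as relative efficacy.** If both arms have the same true fall and each paired test is significant with probability p, exactly one arm is significant with probability 2p(1 − p):

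| p | One arm significant, the other not |
|---|---|
| 0.05 (no fall in either arm) | 9.5% |
| 0.50 | 50% |
| 0.80 | 32% |

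Half of these would point to doxercalciferol. In simulation, equal falls of 0.2 to 0.5 SD gave discordance from 3.0% (r = 0.7, fall 0.5 SD, paired power near 100%) to 49.5% (r = 0.5, fall 0.3 SD). The size therefore depends on paired power, which the protocol does not give.

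**Step 4: the other outcomes at 0.05.** For five laboratory outcomes (iPTH, calcium, phosphate, hypercalcaemia, hyperphosphataemia):

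- If independent: 1 − 0.95⁵ = 22.6%.
- With a common correlation of 0.7: 14.9%.
- If the two binary tests have a true size of about 2.5%, because Fisher's test is conservative: 1 − 0.95³ × 0.975² = 18.5%.

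These are chances of any significant difference, in either direction, on any outcome. They are not chances of a false claim about PTH.

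**The case against.** The best defence is that the decisive comparison can be inferred. PTH is the only outcome named in the title, hypothesis and sample size. Laboratory values are planned only at baseline and 12 weeks. Both the Summary and 5.12 name a between-arm test. A threshold of 0.05 per test does not say that every test is confirmatory, and multiplicity for secondary outcomes is often left to a statistical analysis plan, which may exist here. The sentence in 5.11 can also be read as comparing changes between arms. Much of this stands, and it limits what may be claimed.

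A reader might infer more from the text than it supports:

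- **That the trial has no main outcome.** It has one. What is missing is its form and the designated test.
- **That there are three between-arm versions of iPTH.** The reduction in objective 1 and the comparison with baseline in 5.11 can be the same quantity. The documents support two versions, level and change. Percent change is not a planned outcome; the 40% suppression figure is background in the Introduction.
- **That a false claim of effectiveness has a chance of about 20%.** Such a figure pools calcium and phosphate with iPTH, assumes independence and counts both directions.
- **That each adverse-event item on the case record form is tested.** Objective 4 promises a comparison of adverse events; row-by-row testing is nowhere stated.
- **That a joint false claim is as likely as either half.** The Summary's conclusion requires effectiveness and safety together, which is rarer by chance, although no decision rule enforces it.

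The defence does not settle the choice between level and change. It also does not remove the conflict between 5.11, which speaks of relative efficacy, and 5.12, whose only test against baseline is within arm. An analysis plan that named one confirmatory test would have to depart from the Summary's rule for all analyses.

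**Conclusion.** The point holds in a limited form. The protocol leaves the deciding iPTH comparison open between level and change, and 5.11 with 5.12 permits a superiority claim from tests that do not compare the arms. The part that can be sized with fewest assumptions is the choice between week-12 level and absolute change. That choice gives about 8% to 9% false positives two-sided, and about 4% to 5% in favour of doxercalciferol against 2.5%, assuming 43 per arm, correlation 0.3 to 0.7 and CV 0.26 to 0.5.

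The further rise from paired tests or from other outcomes is real, but no single figure can be given for it. It depends on paired power, on correlations, and on whether discordant paired results would be read as superiority. This is a wording defect that should be corrected; it does not invalidate the design.

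**What to change.** State in 5.11, 5.12 and the Summary that the primary endpoint is iPTH at 12 weeks. The single confirmatory test is the between-arm difference adjusted for baseline iPTH (ANCOVA, on the log scale if skewed, by a rule set in advance), two-sided 0.05. Then:

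- Reword the 5.11 sentence so that relative efficacy rests on this between-arm test.
- Make the within-arm paired tests descriptive only.
- Report calcium, phosphate, hypercalcaemia, hyperphosphataemia and adverse events as secondary, with 95% confidence intervals.
- Limit the p<0.05 sentence to the primary test in both the Summary and 5.12; changing only one leaves the other in force.

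On a given scale, ANCOVA gives the same treatment p-value for the week-12 value as for the change, so the choice between them disappears. It also keeps the quantity used in 5.8, a difference in level. With equal variances, its error variance is about (1 − r²) of that for level alone, or 0.91 to 0.51 for r of 0.3 to 0.7, so it needs no more patients. The baseline is already collected, and no visit or assay is added. The open choice of analysis set must be settled separately before the test is fully fixed.

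The cost is a few sentences of wording, and secondary results no longer support confirmatory claims.
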